3.5 Data Analysis

Chemosensitivity will be measured using a 100mmVAS anchored at each end (left end:No symptoms, right end: Severe symptoms). The distribution of this measure will be checked for its approximation to a gaussian distribution. An analysis to provide preliminary data for a new grant submission will be examined after approximately 15 subjects (5 DM, 10 controls) have completed the studies, but there is no intention of stopping the study based on the preliminary results. We anticipate conducting this analysis in July 2014 or thereafter.

Question	Summary Parameter	Statistical analysis
Sensation (symptoms) during enteral infusion (Aim 1)	VAS score	i) compare VAS scores in response to lipid infusion + exendin vs. lipid infusion + placebo separately for each group using a 2-sample t-test or Wilcoxon rank sum test ii) compare the delta VAS scores (exendin – placebo) to assess the association with subject status (FD,DM, and controls) using an ANOVA model (adjusting for covariates, eg, type of DM) or Kruskal-Wallis test.
Relationship between intestinal chemosensitivity and severity of ongoing upper GI symptoms	Mean symptom score and QoL defined by the Nepean dyspepsia index and GCSI diary	Multiple linear regression with the dependent variable = mean symptom score, and separately the QoL score (possibly after rank transformation). Potential predictor variables = VAS score during enteral lipid + placebo infusion, gastric emptying, age, gender, BMI
Relationship between sensation and plasma hormones during lipid infusion (Aim 2)	Using the VAS score from the enteral infusions and for hormones, the AUC values	Spearman correlations between the VAS score and the AUC values for the various hormones, overall and separately by group (FD,DM, controls)
Small intestinal tight junction proteins,	Protein expression, lactulose:mannitol	Assess the associations between permeability and protein expression, vs. the VAS score, based on Spearman

permeability, intestinal chemosensitivity	ratio, VAS score	correlations.
---	------------------	---------------

The sample size estimate is based on our previous study which evaluated intestinal chemosensitivity in functional dyspepsia in which the proportions with severe symptoms were assessed. [In the current proposal, symptoms during lipid infusion will be evaluated on a continuous VAS scale, likely providing the ability to detect smaller effect sizes]. The effect of lipid plus

Group	Proportions (%) with severe symptoms			
	exendin+lipid vs. placebo+lipid	Controls vs. FD (exendin+lipid)	Controls vs. DM (exendin+lipid)	FD vs. DM (exendin+lipid)
Controls(n=12 vs n=12)	10% vs. 68%	10% vs. 60%	10% vs. 60%	30% vs. 73%
functional dyspepsia (n=20 vs. 20)	10% vs. 50%			
DM (n=20 vs. 20)	10% vs. 50%			

placebo vs. lipid plus exendin in response to enteral infusion can be based on a comparison of the proportions with severe symptoms using a two sample t-test. The association of group status with response to lipid plus exendin can also be assessed using a two-sample t-test for proportions. There is ~80% power (alpha =0.05, 2-sided) to detect the specified differences listed in the table below.

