A recent study suggests that patients with functional dyspepsia have low-grade mucosal inflammation, abnormalities of cell-to-cell adhesion proteins which predispose to increased epithelial permeability, and a leaky epithelial barrier¹⁶. Type 1 DM is associated with increased small intestinal permeability even in subjects who do not have celiac disease^{17,18}. Moreover, a comparison of 339 type 1 DM patients and 89 first degree relatives observed higher serum zonulin levels in type 1 DM patients than controls or relatives; patients with increased zonulin had increased epithelial permeability¹⁹. The only study which evaluated small intestinal permeability in type 2 DM used suboptimal techniques and reported normal permeability²⁰.

Our *overall hypothesis* is that intestinal chemosensitivity related to increased epithelial permeability and CCK explains symptom severity in patients with DM with upper GI symptoms.

The **specific aims** of this study are to address the following hypotheses in 24 healthy subjects, 40 patients with DM and GI symptoms, and 40 patients with functional dyspepsia:

- 1) **A) Patients with DM and GI symptoms have increased intestinal chemosensitivity compared to controls and B) Intestinal chemosensitivity predicts severity of ongoing upper gastrointestinal symptoms independent of gastric emptying.** Intestinal chemosensitivity will be recorded by evaluating symptoms during duodenal lipid infusion (222 kcal, 222 ml) and placebo or the GLP-1 receptor antagonist exendin 9-39 over 2 hours; plasma hormones (i.e., glucose, CCK, GLP-1, PYY, C-peptide, will also be measured. Delivering nutrients into the duodenum will ensure that hormonal responses are not affected by gastric emptying disturbances. Day-to-day symptoms will be evaluated by the Nepean dyspepsia severity index and the GCSI. The relationship between daily symptoms and intestinal chemosensitivity will be assessed in a model which also incorporates gastric emptying and accommodation.

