8. For two days prior to studies, subjects will be instructed to avoid ingestion of artificial sweeteners such as SplendaTM (sucralose), NutrasweetTM (aspartame), foods containing lactulose or mannitol
9. Pregnant or breast-feeding females
10. Known intolerance or allergy to eggs
11. Poor peripheral venous access, if central venous access is not available
12. Any other condition or prior therapy that, in the opinion of the investigator, would make the patient unsuitable for the study

Exclusion criteria for controls only

1. Current symptoms of a functional gastrointestinal disorder assessed by questionnaire

Exclusion criteria for patients only

1. Severe vomiting that would preclude tube placement or participation in the study
2. Structural cause for symptoms by endoscopy within the past 48 months
3. Patients with gastric pacemakers

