v) Hormonal responses and symptoms during duodenal infusions. A small bore nasogastric tube will be inserted through the nostril into the stomach over a guidewire and advanced under fluoroscopic guidance until the infusion ports are in the 2nd part of the duodenum.

Thereafter, subjects in each group (ie, functional dyspepsia and DM) will be randomized to lipid infusion {66.7 mL Microlipid (0.5 gm/mL diluted in water to 222 ml)} together with placebo or exendin 9-39 in the ratio of 1:1. Lipids will be delivered into the duodenum at an infusion rate which matches the rate at which glucose enters the systemic circulation after oral glucose. After placement of an IV in the hand or forearm vein for blood draws, this hand will be placed in a hotbox heated to 55°C. We have considerable preliminary data for symptoms and hormonal responses with this paradigm. Plasma glucose, insulin, C-peptide, GLP-1, CCK, ghrelin, and PYY will be collected at 5 minute intervals for 30 minutes, 10 minute intervals from 30 – 60 minutes, and at 15 minute intervals from 60 – 180 minutes (18 times including 0 minutes).

vi) GLP-1 antagonist exendin 9-39 will be sourced from C.S. Bio, reconstituted in the Mayo Pharmacy by an established process used in previous studies, and undergo endotoxin testing, sterility testing and bacterial testing, and held in quarantine before it will be used in humans. Research compounded sterile preparations (CSP) are prepared and assessed for end preparation testing according to USP <797> in the hospital pharmacy services production lab. Each batch is tested for sterility according to USP <71> utilizing membrane filtration. The sterility testing is validated by a formulation Bacteriostasis Fungistasis test. The amount of each batch tested is determined by USP <71>. Each batch is tested for endotoxin according to USP <85>. High risk CSP are quarantined for 14 days and when all end preparation testing is completed.

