3.6 Potential Pitfalls

To reduce the likelihood of patient intolerance, a smaller diameter tube will be used for enteral nutrient infusion. Only lipid and not carbohydrate infusions will be given; hence the duration of this study is shorter and hyperglycemia during nutrient infusion is less likely.

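### Chemosensitivity is taken from the VAS during lipid infusion with no pre-infusion rating scheduled or used, so background dyspepsia can enter the non-randomised analyses (Aims 1A, 1B, 2A and 3B)

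*Combined protocol and SAP*

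**What the plan says.** - **Measure.** Section 3.5: "Chemosensitivity will be measured using a 100mmVAS anchored at each end (left end:No symptoms, right end: Severe symptoms"). Aim 1 in Section 1: "Intestinal chemosensitivity will be recorded by evaluating symptoms during duodenal lipid infusion (222 kcal, 222 ml) and placebo or the GLP-1 receptor antagonist". The placebo named there is the comparator for intravenous exendin, not for lipid.
- **Arms.** Section 3.3 v) gives every randomised subject lipid, "together with placebo or exendin 9-39 in the ratio of 1:1". Section 3.6 adds: "Only lipid and not carbohydrate infusions will be given". No saline or other nutrient-free duodenal infusion appears.
- **Timing.** Section 3.3 v) sets out a blood schedule that ends "at 15 minute intervals from 60 – 180 minutes (18 times including 0 minutes"). It gives no symptom schedule for the infusion. VAS times (every 15 minutes, six symptoms) are given only for the gastric emptying day, in 3.3 viii).
- **Analyses.** In the 3.5 table, the summary parameter for Aim 1 is just the VAS score. The only delta is exendin minus placebo. For Aim 1B the potential predictors of daily symptoms are "VAS score during enteral lipid + placebo infusion, gastric emptying, age, gender, BMI". The rows for plasma hormones (Aim 2) and for permeability and tight junction proteins correlate those measures with the same VAS score.
- **Groups.** Section 3.2 requires dyspepsia symptoms in patients. For controls it excludes "Current symptoms of a functional gastrointestinal disorder assessed by questionnaire".

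**The concern.** A VAS rating taken during the infusion is the sum of symptoms already present, discomfort from the tube and the earlier tests that day, and the response to lipid. Only the last of these is chemosensitivity. The first differs between patients and controls because of the entry criteria, and among patients it is likely to track daily symptom severity.

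Two consequences follow. In Aim 1B, daily symptom scores are regressed on a predictor that may contain the same ongoing symptoms, so an association can appear with no link to lipid. Gastric emptying, age, gender and BMI do not measure symptoms at the time of infusion and cannot remove it. In Aim 1A, patients with diabetes can score higher than controls although their response to lipid is identical. The correlations of VAS with hormones (2A) and with permeability markers (3B) are open to the same mixing.

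A rating that was not taken before the infusion cannot be recovered later.

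**Working it through.** **The plan's own figure.** Section 3.5 states about 80% power at two-sided 0.05 for differences in the proportion with severe symptoms. A pooled z-test gives 81.3% for 10% vs 50% (20 vs 20), 80.0% for 30% vs 73% (20 vs 20), 85.5% for 10% vs 60% (12 vs 20) and 88.2% for 10% vs 68% (12 vs 12). The statement is roughly reproduced, and nothing below depends on it.

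**Inputs from the documents.** Arm sizes are 12 controls, 20 functional dyspepsia and 20 diabetes per treatment, with two-sided alpha 0.05. The lipid + placebo arm therefore holds 20 patients with diabetes, 20 + 20 = 40 patients, or 12 + 20 + 20 = 52 subjects with controls included. The plan does not say which set the Aim 1B regression uses.

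**Inputs assumed.** The documents give no VAS SD, no background level and no correlation of background with daily symptoms. All three are varied.

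**Aim 1B.** Let the background make up a share s of VAS variance and correlate r with the daily score, and let the lipid response be unrelated to the daily score. The correlation induced between VAS and daily score is ρ = r√s. With z = atanh(ρ)·√(n − 3), the chance of a significant result is Φ(z − 1.96) + Φ(−z − 1.96).

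Example: r = 0.5, s = 0.25, n = 40. Then ρ = 0.5 × 0.5 = 0.25, z = 0.2554 × √37 = 1.554, and the probability is 0.34.

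| r | s | n = 20 | n = 40 | n = 52 |
|---|---|---|---|---|
| 0.3 | 10% | 7% | 9% | 10% |
| 0.3 | 30% | 10% | 17% | 21% |
| 0.3 | 50% | 14% | 26% | 33% |
| 0.5 | 10% | 10% | 16% | 20% |
| 0.5 | 30% | 21% | 40% | 50% |
| 0.5 | 50% | 33% | 61% | 74% |

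The nominal rate is 5%. Direct simulation of the correlation test agrees to about one percentage point.

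**Aim 1A.** Take 20 diabetes vs 12 controls in one arm, an identical lipid response, and a mean background gap δ. The t-test has 30 degrees of freedom, critical value 2.042 and noncentrality δ / [SD × √(1/12 + 1/20)] = δ / (0.365 × SD).

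| δ | SD 20 mm | SD 25 mm |
|---|---|---|
| 2 mm | 6% | 6% |
| 5 mm | 10% | 8% |
| 10 mm | 26% | 19% |
| 15 mm | 51% | 36% |
| 20 mm | 75% | 56% |

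**Does a time-0 rating help when it is itself noisy?** A separate simulation (1,500 runs per setting) gave every group the same lipid response (mean 15 mm, SD 15) and each rating an error SD of 8 mm. Mean background in patients was 10 to 30 mm (2 mm in controls), and background correlated 0.3 or 0.6 with daily score.

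| Analysis | Raw VAS | Change from time 0 | Time 0 as covariate |
|---|---|---|---|
| 1B, 40 patients, r = 0.3 | 16–18% | 4–5% | 5–7% |
| 1B, 40 patients, r = 0.6 | 44–58% | 4–6% | 12–14% |
| 1A, 20 vs 12 | 21–97% | 4–6% | not run |

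With background equal at 2 mm in all groups, the raw Aim 1A test rejected in 4.7% of runs. The randomised exendin-placebo contrast within a group rejected in 5.4% of 4,000 runs under its null.

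**The case against.** Four points on the other side carry weight.

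1. **Silence is not absence.** The plan gives no VAS times, summary or baseline rule for the infusion, and Section 3.3 v) refers to an established paradigm with preliminary symptom data. A reader might infer that no baseline is taken. The documents do not say so. They show only that none is scheduled and that no analysis in 3.5 uses one; even a rating that was taken would not help under the current text.
2. **The drug comparison stands.** A reader might infer that Aim 1 as a whole, or the exendin effect, is biased. It is not. Both statistical tests listed in 3.5 for sensation during the infusion are exendin-placebo contrasts. Background has the same expectation in both randomised arms and cancels. The same holds for Aim 2B. A direct diabetes-control test of VAS is not listed in that table; it is implied by the Aim 1A hypothesis and by the power table, where it is posed as proportions with severe symptoms under exendin + lipid.
3. **Background may be low.** Subjects fast overnight before the infusion, and early satiety and postprandial discomfort, two of the five symptoms named for entry, are meal-related. If backgrounds are nearly equal, the Aim 1A error stays near 5%. Without a rating, however, nobody can show that this was so.
4. **The predictor list is open.** It is headed as potential predictors, so a baseline term could still be added, but only if it has been recorded.

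**Conclusion.** The concern holds for the non-randomised uses of the infusion VAS: the Aim 1B regression, the comparison implied by Aim 1A, and the correlations for 2A and 3B. It does not hold for the randomised exendin-placebo contrasts.

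The size is uncertain because every driver is an assumption. The Aim 1B false-positive rate runs from about 7% (n = 20, correlation 0.3, background 10% of VAS variance) to 74% (n = 52, correlation 0.5, background 50%). The upper end requires controls to be pooled into the regression, which the plan does not state. For Aim 1A at SD 20 mm the range is 6% to 75% over background gaps of 2 to 20 mm. It would be going too far to say that Aims 1A and 1B will come out positive without any chemosensitivity: the documents show that they could, not how likely it is.

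This is a should-fix point. The remedy is cheap, but the affected analyses are associational and the drug contrast is sound.

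**What to change.** - **Section 3.3 v):** record the same 100 mm VAS once after tube placement and before lipid and study drug start, at the time-0 blood sample. State the rating times during the infusion and how they are summarised.
- **Section 3.5:** for Aims 1A, 1B, 2A and 3B, define chemosensitivity as the infusion VAS minus the time-0 VAS, or enter time-0 VAS as a covariate. Report the raw level as secondary. Add the diabetes-control comparison for Aim 1A to the analysis table, and say whether the Aim 1B regression includes controls.
- **Randomised exendin-placebo contrast:** time-0 VAS is optional here, as a covariate for precision only.

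**Cost.** One extra rating per subject at an existing time point, plus text. A change score carries some added measurement noise. Covariate adjustment with a noisy baseline leaves some residual bias in Aim 1B (5% to 14% in the simulation above, against 16% to 58% for raw VAS). Neither option separates lipid from volume or expectation effects, because a time-0 rating does not replace a nutrient-free control infusion. That limit should be stated in the report.

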Hence, we propose to evaluate the overall hypothesis that intestinal chemosensitivity related to increased epithelial permeability and GLP-1 explains symptom severity in patients with functional dyspepsia and in patients with DM and dyspepsia. 24 healthy subjects, 40 patients with DM and GI symptoms, and 40 patients with functional dyspepsia will undergo assessment of intestinal chemosensitivity during duodenal nutrient perfusion, gastric emptying (by scintigraphy), cardiovascular and GI vagal functions (plasma pancreatic polypeptide response to sham feeding and a comprehensive autonomic reflex screen), in vivo assessment of small intestinal permeability (urinary lactulose:mannitol ratio), and upper endoscopy with assessment of epithelial tight junction proteins and permeability on small bowel biopsies. During the nutrient infusion, subjects in each group (ie, healthy subjects, functional dyspepsia and DM) will be randomized to lipid infusion and placebo or lipid infusion {66.7 mL Microlipid (0.5 gm/mL diluted in water to 222 mL)} and exendin 9-39 in the ratio of 1:1. Hormonal responses (i.e., GLP-1, CCK, GIP, glucagon, PYY, C-peptide, and insulin) and plasma glucose will also be evaluated during enteral nutrient infusion. GI symptoms during each perturbation (meal, nutrient infusion) will be evaluated by validated questionnaires. Blood will be collected for DNA-based genetic analyses, initially to assess the relationship of GI sensorimotor dysfunctions and symptoms with SNPs affecting CCK and GLP-1 receptors. The analysis will assess for disturbances in these parameters in functional and DM dyspepsia, investigate associations between symptoms during enteral infusion and hormonal-epithelial functions, and evaluate relationships between daily symptoms and results of testing.

Table of Contents

ABSTRACT.....	1
1 SPECIFIC AIMS	3
2 BACKGROUND AND SIGNIFICANCE.....	5
3 RESEARCH DESIGN AND METHODS.....	7
3.1 Study Design.....	7
3.2 Study Subjects.....	7
3.3 Details of Study Assessments	8
3.4 Gene and Epigenetic Studies	15
3.5 Data Analysis	16
3.6 Potential Pitfalls.....	17
4 HUMAN SUBJECTS	17
5 SAFETY AND ADVERSE EVENTS	19
5.1 Definitions.....	19
5.2 Recording of Adverse Events	21
5.3 Reporting of Serious Adverse Events and Unanticipated Problems.....	22
5.3.1 Sponsor-Investigator reporting: notifying the Mayo IRB.....	22
5.3.2 Sponsor-Investigator reporting: Notifying the FDA.....	22
5.4 Stopping Rules	23
5.5. Medical Monitoring	23
APPENDIX.....	23

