- 2) **Intestinal chemosensitivity will be A) associated with higher plasma CCK and GLP-1 concentrations B) reduced by the GLP-1 antagonist exendin 9-39 and C) inversely associated with impaired abdominal vagal function.** This hypothesis will be evaluated by comparing intestinal chemosensitivity (a) with plasma CCK and GLP-1 concentrations (b) with and without exendin 9-39 and (c) in patients with and without and GI vagal dysfunction as assessed by the plasma pancreatic polypeptide response to sham feeding.
- 3) **A) Patients with DM and GI symptoms have abnormal epithelial tight junction proteins which predispose to increased epithelial permeability and increased small bowel permeability and B) These structural and functional markers of epithelial permeability are associated with intestinal chemosensitivity.** Intestinal permeability will be measured in vivo by two sugar urine excretion after oral ingestion. Biopsies from the distal second or third portion of the duodenum will be obtained endoscopically, to measure various markers of epithelial structure and function.

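### The randomised exendin hypothesis (Aim 2B) is tested only in three separate groups, with no overall estimate, no deciding test and no error control

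*Combined protocol and SAP*

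**What the plan says.** Section 1, Aim 2, part B predicts that chemosensitivity will be "reduced by the GLP-1 antagonist exendin 9-39". It names no group. The abstract frames the overall hypothesis for patients with functional dyspepsia and patients with diabetes and dyspepsia. It says that "subjects in each group (ie, healthy subjects, functional dyspepsia and DM) will be randomized to lipid infusion and placebo or lipid infusion" with "exendin 9-39 in the ratio of 1:1".

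The first row of the analysis table in section 3.5 holds the only planned comparisons of exendin with placebo:

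- Item (i) will "compare VAS scores in response to lipid infusion + exendin vs. lipid infusion + placebo separately for each group", by a two-sample t-test or Wilcoxon rank sum test.
- Item (ii) will "compare the delta VAS scores (exendin – placebo) to assess the association with subject status (FD,DM, and controls) using an ANOVA model", or a Kruskal-Wallis test.

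The power table in section 3.5 follows the same split: 12 vs 12 controls, 20 vs 20 FD and 20 vs 20 DM. The text says of it: "There is ~80% power (alpha =0.05, 2-sided) to detect the specified differences listed in the table below".

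No pooled or group-stratified exendin test, no deciding group and no multiplicity rule appears in the document. By contrast, the hormone-correlation row of the same table plans both an overall and a by-group analysis.

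**The concern.** Exendin against placebo is the only randomised contrast in the study. A single hypothesis is put to three independent tests, and nothing says how the three results combine into one answer. With one significant group and two non-significant ones, the plan would equally permit the report that Aim 2B is confirmed, refuted or true for one population only.

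Item (ii) does not settle this. It asks whether the exendin effect differs between groups, not whether there is one. It is also built on a difference between exendin and placebo scores, and each subject receives only one of the two infusions. No subject has such a difference, so the ANOVA or Kruskal-Wallis test cannot be run as written.

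**Working it through.** **Inputs from the documents.** Subjects per arm: 12 (controls), 20 (FD), 20 (DM). Two-sided alpha 0.05. Severe-symptom rates, exendin vs placebo: 10% vs 68% in controls and 10% vs 50% in both FD and DM (power table, section 3.5).

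**Input assumed.** The plan gives no SD or target difference for the VAS, so effects d are in SD units, with 0.5, 0.6 and 0.8 as a range. The effect and the SD are taken as common to the groups.

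**1. The plan's own power figure.** Pooled-variance formula for two proportions:

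power = Φ{[|p1 − p2| − 1.96·√(2p̄(1 − p̄)/n)] / √[(p1(1 − p1) + p2(1 − p2))/n]}

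- FD or DM, 10% vs 50%, n = 20: (0.40 − 1.96 × 0.1449)/0.1304 = 0.89, power 81.3%.
- Controls, 10% vs 68%, n = 12: (0.58 − 1.96 × 0.1991)/0.1601 = 1.18, power 88.2%. Fisher's exact test gives 79.3%.

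Each entry agrees with about 80% under a standard method. The differences concerned are 40 and 58 percentage points.

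**2. False-positive risk if any significant group counts.** The groups contain different people, so independence is reasonable.

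- Either direction: 1 − 0.95³ = 14.3%.
- Reduction only, as Aim 2B predicts: 1 − 0.975³ = 7.3%, against 2.5% for one test.

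Section 3.3, item (v), names only FD and DM as randomised. On that reading there are two tests, and the two-sided figure is 1 − 0.95² = 9.75%. The abstract and the 12 vs 12 row of the power table support three.

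**3. Power on the VAS.** Noncentral t with 2n − 2 degrees of freedom and noncentrality d·√(n/2).

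| d (SD) | Controls, 0.05 | FD or DM, 0.05 | Any of three, unadjusted | Any of three, Bonferroni (0.0167 each) | FD+DM, 40 vs 40, 0.05 |
|---|---|---|---|---|---|
| 0.5 | 22% | 34% | 66% | 42% | 60% |
| 0.6 | 29% | 46% | 79% | 57% | 76% |
| 0.8 | 47% | 69% | 95% | 83% | 94% |

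The any-of-three columns are 1 − (1 − power in controls)(1 − power in FD)(1 − power in DM). At d = 0.6:

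- Unadjusted: 1 − 0.710 × 0.544² = 0.79.
- Bonferroni, where the separate powers are 15.4%, 28.5% and 28.5%: 1 − 0.846 × 0.715² = 0.57.

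**4. When averaging hurts.** Suppose the effect is 0.8 SD in one patient group and zero in the other. The average is 0.4 SD, and power at 40 vs 40 is 42%. The affected group tested alone at 0.05 has 69%.

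**The case against.** Analysis by group is a defensible choice. FD, DM and healthy controls are different populations, each group is sized separately, and the study is mechanistic with no declared primary endpoint. If exendin acts in only one patient group, an averaged test is the weaker one (step 4). This stands, and it is why the group estimates must remain in the report.

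A reader might infer that the plan suffers the power loss and the 14.3% error together. It does not. Counting any significant group gives at least the power of the FD+DM test (79% vs 76% at 0.6 SD) but raises the error. The marked loss comes only when the error is controlled or one group must decide alone. Nor does low power within each group mean that the study as a whole would probably miss a moderate effect.

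A reader might also infer that the stated power of about 80% is wrong. It reproduces, for large differences. If severe symptoms are a cut on a normal scale (an assumption), 10% vs 50% corresponds to about 1.28 SD. Power on the continuous score is then about 98% at 20 per arm, and the choice of test hardly affects power. The plan does, however, expect the VAS to pick up smaller effects, and there the choice matters.

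Finally, controls should not be set apart on the ground of a floor effect. The power table assumes 68% with severe symptoms in placebo controls, above the 50% assumed for patients.

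**Conclusion.** The concern holds as a gap in how Aim 2B is to be concluded. The plan has no overall estimate of its one randomised effect and no rule for combining three tests, and its between-group comparison cannot be computed as written. The cost depends on the rule adopted later:

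- **Any significant group counts:** the two-sided error is 14.3%, or 7.3% instead of 2.5% for falsely confirming a reduction, with little loss of power.
- **Error controlled by Bonferroni:** 11 to 19 percentage points of power are lost against one FD+DM test over 0.5 to 0.8 SD (83% vs 94%, 57% vs 76%, 42% vs 60%).

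The power comparison rests on assumed SD-unit effects and on similar effects in FD and DM. The plan makes the second assumption itself, with identical rates of 10% vs 50% in both. The gap should be closed before unblinded analysis, but it does not invalidate the design or the sample size.

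**What to change.** Replace items (i) and (ii) with one linear model of the VAS score on arm, group and arm-by-group interaction.

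- **Deciding test for Aim 2B:** the exendin effect averaged over FD and DM (40 vs 40), two-sided 0.05. If the VAS is not Gaussian, use a van Elteren test stratified by group (FD, DM).
- **Secondary:** the arm-by-group interaction, which is what item (ii) was meant to assess, and the exendin estimate with confidence interval in each of the three groups.
- **Rationale to state:** FD and DM are averaged because the plan assumes the same effect in both. Controls are reported separately because the overall hypothesis concerns patients.
- **Label:** tie this comparison to Aim 2B; the row is now headed Aim 1.

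The cost is analysis wording only, with no added subjects, visits or data. The downside is the dilution in step 4 if exendin works in only one patient group, so the interaction and group estimates should be reported whatever the deciding test shows.
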